### **4. BLINDING**

D-CARE is an unblinded trial; however, all baseline and follow-up data collection will be completed by blinded site staff.

At the Data Coordinating Center, [name] will be the blinded statistician who will interface with the study leadership and attend the open session of the DSMB meetings; [name], [name], [name], [name], [name] and [name] will be the unblinded statisticians who will prepare the randomization scheme and the closed DSMB report as well as attend the closed DSMB sessions.

### **5. OUTCOME MEASURES**

#### **5.1 Schedule of Administration**

The primary, secondary, and tertiary outcomes are summarized in Table 1 along with their schedule of administration. Most of these outcomes are patient-reported and all are clinically meaningful to patients and caregivers as well as payers.

**Table 1. Outcome Domains, Instruments and Timing**

Measure	Administration	Month				
		Baseline (in-person)*	3 (phone)	6 (phone)	12 (phone)	18 (phone)
Sociodemographic characteristics		X				

Primary outcomes						
NPI-Q Severity (patient behaviors)	Questionnaire	X	X	X	X	X
Caregiver strain (MCSI)	Questionnaire	X	X	X	X	X
Secondary Outcomes						
NPI-Q Distress (caregiver)	Questionnaire	X	X	X	X	X
Caregiver depression (PHQ-8)	Questionnaire	X	X	X	X	X
Caregiver self-efficacy	Questionnaire	X		X		X
Tertiary Outcomes						
Cognition (MOCA)	Interview	X				X
Functional status (FAQ)	Interview	X				X
Functional status (Katz ADL)		X				X
Goal attainment scaling ***	Interview	X		X		X
Mortality	CMS					X
	Interview		X	X	X	X
Time spent at home	CMS					X
Inpatient hospital use**	CMS					X
Acute inpatient rehabilitation use**	CMS					X
Post-acute SNF use**	CMS					X
Hospice use**	CMS					X
Long-term nursing home use**	CMS					X
Caregiver Rating of Dementia Care Quality	Questionnaire				X	
Caregiver satisfaction with dementia care	Questionnaire		X		X	X
Dementia Burden Scale-Caregiver	Composite	X	X	X	X	X
Clinical Benefit	Composite	X	X	X	X	X
Quality of Life in Alzheimer's Disease	Questionnaire	X				X
Positive Aspects of Caregiving	Questionnaire	X		X		
Cost-effectiveness analysis	CMS					X

CMS=Center for Medicare and Medicaid Services and site-obtained claims data;

\*Switched to telephone-collected after beginning of COVID-19 pandemic, with option for in-person visits

\*\* Also used to calculate time spent at home

\*\* Goal Attainment Scaling will be obtained only on a subset of caregivers (i.e., it will not be performed in caregivers in the usual care group nor on all caregivers in the two active intervention groups; this will be completed by an unblinded assessor (i.e., the Dementia Care Specialist or Care Consultant) with goal setting occurring at baseline, and goal attainment scaling occurring 6 months [6-12 months window] and 18 months [15-18 months window] after enrollment).

## **5.2 Primary Outcomes**

There are two primary outcomes in D-CARE measuring dementia-related behavioral symptoms and caregiver distress at 3, 6, 12 and 18 months after baseline.

### 1. Severity of Dementia-related Behavioral Symptoms

The severity of symptoms of psychopathology in persons with dementia will be measured by the Neuro-Psychiatric Inventory Questionnaire - Severity (NPI-Q Severity). The NPI-Q Severity is a validated survey that assesses the caregiver's perception of the severity of 12 dementia-related psychiatric and behavioral symptoms. NPI-Q Severity scores range from 0-36 with higher scores indicating more severe symptoms.

### 2. Caregiver Distress

The level of caregiver distress/strain as measured by the Modified Caregiver Strain Index (MCSI). The MCSI is a 13-item validated tool used to assess severity of caregiver strain. The index targets financial, physical, psychological, and social aspects of strain and is scored from 0 to 26 with higher scores indicating greater levels of strain.

## **5.3 Secondary Outcomes**

There are three secondary outcomes in D-CARE:

### 1. NPI-Q Distress (measured at 3, 6, 12 and 18 months after baseline)

Distress of caregivers due to the symptoms of psychopathology in persons with dementia will be measured by the Neuro-Psychiatric Inventory Questionnaire - Distress (NPI-Q Distress). The NPI-Q Distress scale is a validated survey that assesses the level of distress experienced by the caregiver in response to dementia-related psychiatric and behavioral symptoms. NPI-Q Distress scores range from 0-60 with higher scores indicating more severe distress.

### 2. Caregiver Depression (measured at 3, 6, 12 and 18 months after baseline)

The severity of depression in caregivers as measured by the Patient Health Questionnaire (PHQ-8). PHQ-8 is a shortened version of the PHQ-9 (item 9 is omitted) that is often used when the instrument is administered by telephone and intervention cannot be adequately provided. The PHQ-9 is 9-item validated tool used to assess depressive symptoms in the caregiver using the DSM-IV criteria for major depression and is scored from 0-27 with scores >10 indicating moderate symptoms and scores >20 indicating severe depressive symptoms. Because of the infrequency of positive responses to item-9, its deletion has minimal effect on scoring and identical scoring thresholds for depression severity can be used.

3. Caregiver Self-Efficacy (measured at 6 and 18 months after baseline)

Caregivers' ability to manage dementia-related problems and ability to access help is measured with a 4-item self-efficacy scale [range, 1 (strongly disagree) to 5 (strongly agree)] measuring the caregiver's self-efficacy for caring for the patient with dementia and for accessing help, including community resources. The scores for each of the 4 items are summed to produce an overall caregiver self-efficacy score ranging from 4-20 with higher scores indicating better caregiver self-efficacy; scores  $\geq 15$  indicate high self-efficacy.

### **5.5 Tertiary Outcomes (Exclusive of Cost-Effectiveness Measures)**

The description of tertiary outcomes excludes two cost effectiveness measures that will be analyzed by the D-CARE health economist: Cost-Effectiveness Relative to Severity of Dementia-related Behavioral Symptoms and Cost-Effectiveness Relative to Caregiver Distress.

1. Cognition of Persons with Dementia (measured at 18 months after baseline)

Cognition as measured by the Montreal Cognitive Assessment (MoCA). MoCA is a validated widely used 30-point test (higher is better) of cognition that captures mild cognitive impairment as well as dementia. This will be collected at baseline and at the end of the study to document disease progression. To reduce respondent burden and missing data, we will use a shortened 3-item form for reporting study participant baseline characteristics and measuring decline in cognition, a tertiary outcome. Participants who score 8 or higher on the shortened version will receive the full 22-item telephone MOCA to determine whether they have capacity to provide informed consent.

2. Functional Status (measured at 18 months after baseline)

Functional status will be measured using the Functional Activities Questionnaire (FAQ) ranges from 0 to 30 with higher scores indicating more functional dependence. We will also measure activities of daily living (Katz ADL), which has been validated and is well-established in research and clinical use. Katz ADL ranges from 0-6, with higher scores indicating more functional independence.

3. Goal Attainment Scaling (measured at 6-12 months and 15-18 months after baseline)

Goal attainment scaling (GAS) asks patients and caregivers to select their most important goal and assesses their progress towards meeting it as a result of one of the study's intervention. *Goal attainment scaling*, defined as whether a person's individual goals are achieved as a result of the study intervention, will be measured using a 5-point goal attainment scale. GAS describes the person's expected level of goal achievement over a specified timeframe, ranging from much worse than expected (scored as -2) to much better than expected (scored as +2). Scales are dynamically set according to a person's needs, while measurement of attainment is standardized. Measurement of goal attainment will be performed with caregivers by clinicians involved in the intervention (Dementia Care Specialists and Care Consultants), who are unblinded, and can be performed over the telephone.

4. Mortality (measured over 18 months)

Mortality as measured by interviews at 3, 6, 12 and 18 months. Data will be verified using the Center for Medicare and Medicaid Services at 18 months. For participants who did not complete the 18-month interview, vital status will be investigated using the electronic health records (EHR).

5. Time Spent at Home

Time spent at home is calculated as 540 minus (1) the number of days in a health care facility, including hospital, nursing home, acute rehabilitation, and inpatient hospice, and (2) the number of days not alive.

6. Caregiver Rating of Dementia Care Quality (measured at 12 months)

The outcome is a count of the number of yesses. Caregiver Rating of Dementia Care Quality is a composite instrument of 10 items (with yes or no responses) from the Assessing Care of Vulnerable Elders (ACOVE), Physician Consortium for Performance Improvement (PCPI) and the American Academy of Neurology (AAN) quality measures. The outcome is a count of the number of yesses (range 0-10, higher counts indicate greater caregiver rating of dementia care quality).

7. Caregiver Satisfaction with Dementia Care (measured at 3, 12 and 18 months)

Caregiver's satisfaction with the dementia care program is measured using a 11-item questionnaire, modified from the University of California Los Angeles' Alzheimer's and Dementia Care program, and ranges from 11 to 55 (higher scores indicate greater caregiver satisfaction with the dementia care program).

8. Dementia Burden Scale - Caregiver (measured at 3, 6, 12 and 18 months after baseline)

Dementia Burden Scale-Caregiver (DBS-CG) is a composite of the NPI-Q Distress, MCSI, and PHQ-8 scales with items transformed linearly to be on a 0-100 possible range and then averaged, with higher scores indicating higher caregiver burden. The minimal clinically important difference (MCID) for the DBS-CG is 5 points.

9. Clinical Benefit (measured at 3, 6, 12 and 18 months after baseline)

Clinical benefit is a binary measure of patient symptoms using the NPI-Q severity scale (the only patient outcome anticipated to benefit from the program) and caregiver symptoms using the DBS-CG scale. Benefit on the NPI-Q severity scale is defined as having a score of  $\leq 6$  (the lowest tertile of symptoms) or improving by at least 3 points (the MCID). DBS-CG benefit is defined as having a score of  $\leq 18.8$  (the lowest tertile of symptoms) or improving by at least 5 points (the MCID). Clinical benefit is defined as having benefit on either or both component scales. Defining benefit in this manner captures both preventive (those who have few symptoms at baseline and do not deteriorate) and therapeutic (those who improve) benefit from the program.

10. Quality of Life in Alzheimer's Disease (measured at 18 months after baseline)

Quality of life will be measured at 18 months by the Quality of Life in Alzheimer's Disease (QOL-AD). The QOL-AD is a 13-item instrument scored 4-52 (higher scores indicate better quality of life) that can be administered to persons with dementia and caregivers. It has demonstrated sensitivity to psychosocial intervention correlates with health-utility measures, is widely translated and used internationally and can be used by people with MMSE scores as low as three.

11. Positive Aspects of Caregiving (PAC) (measured at 6 months after baseline)

PAC is measured with 11 items focusing on favorable aspects of the caregiving experience, with range 0-44 (most positive) and Cronbach's alpha 0.92. The items ask about their mental or affective state related to their caregiving experience. For example, providing help to care recipients has 'made me feel more useful', 'made me feel strong and confident', 'given more meaning to my life', 'enabled me to develop a more positive attitude toward life', and 'enabled me to learn new skills'.

12. CMS Patient Outcomes (measured over 18 months)

- 12a. Inpatient Days Spent at an Acute Care Hospital is defined as the number of days an individual is admitted to an acute care hospital.
- 12b. Inpatient Days Spent at an Inpatient Rehabilitation Facility is defined as the number of days an individual is admitted to an inpatient rehabilitation facility.
- 12c. Inpatient Days Spent at a Skilled Nursing Facility is defined as the number of days an individual is admitted to a Skilled Nursing Facility.
- 12d. Inpatient Days Spent at a Long-term Care Facility is defined as the number of days an individual is admitted to a Long-term Care Facility.
- 12e. Placement in Long-term Care Facility, which will be defined by (1) observed placement in a long-term care facility, or (2) the time (days) from enrollment to when individual is admitted to a Long-term Care Facility.
- 12f. Days Spent Receiving Hospice Benefit is defined as the number of days an individual is receiving hospice care regardless of location.

## **6. SAMPLE SIZE**

### **6.1 Primary Outcomes**

The assumptions used to determine sample size for testing differences among the three treatment arms for the two primary outcomes were: 1) type I error  $0.05/6 = 0.0083$  adjusted for 3 treatment comparisons (HSDC vs. CBDC, HSDC vs. UC and CBDC vs. UC) times 2 primary outcomes, 2) standard deviation (SD) for NPI-Q severity of 6.5 units and SD for MCSI of 6.7 units, 3) treatment difference for HSDC vs. CBDC of 1.5 units, 4) treatment difference for HSDC and CBDC vs. UC = 3, and 5) lost to follow up over 18 months because of death and dropout of 25%. The detectable treatment difference of 1.5 units for HSDC vs. CBDC is based on data reported in the literature suggesting a minimally clinical important difference (MCID) ranging from 2.8 to 4.0 (Mao et al., 2015). Given that both intervention arms will be receiving an intervention, we reduced the detectable difference in half to 1.5. Data from two studies (Callahan et al., 2006; [name], 2016) indicate that the expected benefit between HSDC and UC would be 3.2 units for NPI-Q Severity score. Based on these data we used a difference of 3 units for comparisons with UC. The estimates of the standard deviations (SD) for the 18-month NPI-Q Severity score and MCSI are 6.5 and 6.7, respectively, based on UCLA pilot data. An 18-month censoring rate of 25% was assumed because of death (15%) and dropout (10%). The

death rate was taken from fee-for-service claims data on 274 UCLA patients with a mean survival time of 1.5 years.

Sample size was first determined for the comparison between HSDC and CBDC because the effect size is smaller. The goal was to achieve at least 90% overall power for testing both outcomes. Testing each outcome at 95% power with a sample size of 1000 subjects per treatment group (adjusted for censoring) gives at least 90% overall power for testing both outcomes. Given these sample sizes, the sample size is 150 (for UC adjusted for censoring) for comparisons with the two interventions giving an overall power of at least 90%. For conservatism, we assumed the same effect size for both interventions compared with UC even though we hypothesize that HSDC will be superior to CBDC. The total sample size for the trial is 2150 individuals (adjusted for censoring).

**Table 2: Power and Sample Size for the Two Primary Outcomes**

Comparison	Difference to be detected	Power for MCSI	Power for NPI-Q Severity	Overall Power	Adjusted Sample Sizes
HSDC vs. CBDC	1.5	95%	95%	90%	1000 per group
HSDC or CBDC vs. UC	3.0	95%	95%	90%	1000 HSDC and CBDC vs. 150 UC

The inflation of sample size for censoring due to deaths and losses is conservative because the data will be analyzed using longitudinal methods under the MAR assumption that include all available data on each participant. Considering the first patient follow-up for the two primary outcomes is at 3 months, the effective censoring rate for analytical purposes is approximately 5% for the primary analysis (i.e., those without any primary outcome follow-up data).

Heterogeneity of treatment effects (HTE) for the two primary outcomes will be assessed in six subgroups of participants: high vs. low patient function by FAQ, high vs. low patient function by ADL, high vs low NPI-Q Severity, high vs low MCSI at baseline, spouse caregiver vs. other caregiver, and white non-Latino vs. nonwhite or Latino. The study will have approximately 90% power to detect interactions (differences in treatment effects between subgroup categories) of about 3 units for both NPI-Q severity and MCSI for the HSDC vs. CBDC comparisons.

Interactions on the order of about 6 units can be detected with approximately 90% power for comparisons of HSDC and CBDC with UC for the two primary outcomes. These detectable interactions assume a conservative Bonferroni adjusted type I error of  $0.05/(6 \times 3 \times 2) = 0.0014$  per outcome to control for multiplicity. (In the analysis, we will conduct one global test of interaction per subgroup for 6 subgroups). Using an anchor-based approach that compares changes in NPI-Q measures with other clinical measures, the MCID for the severity scale is 3.2 (Mao et al., 2015). Hence, based on this range of MCID, the study will have adequate power to detect clinically meaningful differences in subgroups for comparisons between the two interventions. However, only large interactions can be detected for the comparisons with UC because of the smaller sample size in this arm. Although equal subgroup sample sizes were assumed in the calculations, power will not be greatly affected if the imbalance in subgroup sample sizes is not more extreme than a ratio of 2:1.

## 6.2 Secondary and Tertiary Outcomes

For the three secondary outcomes (NPI-Q Distress, caregiver depression (PHQ-8), Caregiver self-efficacy), we determined the detectable effect sizes assuming a Bonferroni adjusted type I error of  $0.05/(3 \times 3) = 0.006$  to control for multiplicity. The detectable effect sizes with 90% power for the three continuous measures (NPI-Q Distress, caregiver depression (PHQ-8), Caregiver self-efficacy) are on the order of 0.20 for testing HSDC vs. CBDC. For testing HSDC/CBDC vs. UC, there will be approximately 90% power to detect effect sizes on the order of 0.40. Thus, we will have good power to detect small to moderate effects for the three continuous outcomes.

Power determinations for tertiary outcomes were not performed because these are considered exploratory. Sample size and power were calculated using Power and Sample Size (PASS) software (Kaysville, UT, 2013).

The goal attainment scaling (GAS) tertiary outcome will be collected only from caregivers (in the two active intervention groups) enrolled through December 15th, 2020. Goals will be set at baseline and will be assessed at two follow-up time points: at 6-12 months and 15-18 months after enrollment. After considering the expected loss to follow up, we anticipate 80% power (appropriate for a tertiary outcome) to detect a 10% difference between HSDC and CBDC arms.

## **7. INTERIM MONITORING**

Interim monitoring will focus on safety, recruitment, adherence to protocol, baseline comparability of treatment groups, data quality, and uptake of the assigned intervention. A set of monitoring tables will be generated for this purpose (see DSMB Tables, Listings and Figures). Because this is a minimal risk trial and the follow-up period is relatively short (18 months), no monitoring for efficacy or futility is being proposed.

### **7.1 Safety Monitoring**

Because this is a minimal risk trial, we will ascertain self-report (by caregiver) of SAEs of death and hospitalizations at each outcome assessment time point, which will be monitored by the DSMB. At the end of the follow-up, we will confirm any between-group differences in self-reported SAEs by examining data on mortality and hospitalizations from CMS data files and site-obtained utilization data. In addition, if a caregiver's, PHQ-8 score is >14, Research Assistants will immediately (that day) notify the site's clinical director (or covering physician) who can decide on next appropriate steps.

## **8. DATA COLLECTION AND DATA FREEZE**

Data collected from date of study initiation (6/18/2019) to last date of 18-month study follow-up interview (08/21/2023) will be used. The trial database for primary, secondary and safety outcomes was closed/frozen on 4/9/2024 and considered ready for final analysis. Data lock for tertiary outcomes will be done at a later date, e.g., after resolution of fidelity data and receipt of CMS data.

## **9. ANALYSIS PLAN**

This section describes the analysis of the primary, secondary and tertiary outcomes, including safety. The analytic plan will be modified as necessary up to final data lock and before study unblinding. Results will be reported to clinicaltrials.gov within one year of obtaining the primary outcome on the last patient. The trial has been registered on clinicaltrials.gov: NCT03786471.

Data analysis will be performed by the unblinded statisticians from the Data Coordinating Center. Current versions of SAS and R will be used for all analyses.

### **9.1 General Approach.**

Nominal and ordinal categorical variables will be summarized using frequencies and percentages. Continuous variables will be summarized with the following descriptive statistics: N, mean, standard deviation, median, minimum, maximum, interquartile range, and range. Kaplan-Meier methodology will be used to summarize time-to-event variables (e.g., mortality). If estimable, 25th, 50th (median), and 75th percentiles will be presented. No imputation of missing data will be performed for the primary analysis of the primary and secondary outcomes. Diagnostic tests and sensitivity analyses will be performed. Parametric distributional assumptions will be checked. If assumptions fail, other distributions will be considered prior to transformations and non-parametric methods.

### **9.2 Comparability of Baseline Characteristics.**

Distributions of baseline demographic and clinical characteristics will be summarized. Comparability for continuous variables will be examined graphically and by summary statistics (means, medians, quartiles, etc.). Categorical variables will be examined by calculating frequency distributions.

### **9.3 Analysis of Primary Outcomes**

All analyses will be according to intent to treat or as-randomized. The analysis of the two primary outcomes – NPI-Q Severity and MCSI scores – will be done using a constrained longitudinal repeated measures analysis (Fitzmaurice et al., 2011) based on maximum likelihood methods adjusted for the stratified randomization by site. Individuals missing both baseline and all follow-up scores for the primary outcomes will be excluded from the analysis; data for PLWD who had a change in caregiver will be censored at the time of caregiver change. Treatment differences, averaged over all follow-up time points, will be summarized by least square means and 97.5% confidence intervals. Significance testing for each outcome will be done by the Hochberg (1988) procedure using an overall type I error of 2.5% (2-sided) to control for the 3 pairwise treatment comparisons, i.e., testing each outcome at 2.5% will maintain the overall type I error at 5% (2-sided). This analysis will be implemented as a mixed effects repeated measures model which uses all available records under the assumption that visit-specific data are missing at random (MAR). Inclusion of the baseline, 3, 6, 12, and 18-month data as outcomes in the model will assist in meeting the MAR assumption. We will test for the treatment by time interaction at the 10% significance level. If significant, we will also report treatment differences at each time point. We will also examine for treatment by site interactions, although there may not be power to detect them. Sensitivity analyses will investigate the MAR assumption, such as methods that jointly model missingness and outcome distributions, e.g., pattern mixture models (Henderson et al., 2000; National Research Council, 2010).

We will conduct an exploratory analysis to test whether giving any intervention is superior to usual care if there is no significant difference between the two interventions, and if neither intervention is superior to usual care for either or both outcomes. We will test this hypothesis using the same longitudinal repeated measures analysis described for the primary outcomes at the 0.05 (2-sided) level of significance uncorrected for multiplicity. The difference between giving any intervention and usual care will be reported as least square means with 95% confidence intervals.

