8.2 Analysis of Primary, Secondary, and Tertiary Outcomes

8.2.1 Analysis of Primary Outcomes

All analyses will be according to intent-to-treat or as-randomized. The analysis of the two primary outcomes – NPI-Q Severity and MCSI scores – will be done using a constrained longitudinal repeated measures analysis²⁶ based on maximum likelihood methods adjusted for the stratified randomization by site. Treatment differences, averaged over all follow-up time points, will be summarized by least square means and 97.5% confidence intervals. Significance testing for each outcome will be done by the Hochberg procedure²⁷ using an overall type I error of 2.5% (2-sided) to control for the 3 pairwise comparisons, i.e., testing each outcome at 2.5% will maintain the overall type I error at 5% (2-sided). This analysis will be implemented as a mixed methods repeated measures (MMRM) model which uses all available records under the assumption that visit-specific data are missing at random (MAR). Inclusion of the baseline 3, 6, 12, and 18-month data as outcomes in the model will assist in meeting the MAR assumption. We will test for the treatment by time interaction at the 10% significance level. If significant, we will also report treatment differences at each time point. We will also

A PRAGMATIC TRIAL OF THE EFFECTIVENESS AND COST-EFFECTIVENESS OF DEMENTIA CARE/COMPARATIVE EFFECTIVENESS OF HEALTH SYSTEM-BASED VERSUS COMMUNITY-BASED DEMENTIA CARE

examine for treatment by site interactions, although there may not be power to detect them. Sensitivity analyses will investigate the MAR assumption, such as methods that jointly model missingness and outcome distributions (e.g., pattern mixture models).^{28,32}

We will conduct an exploratory analysis to test whether giving any intervention is superior to usual care if there is no significant difference between the two interventions, and if neither intervention is superior to usual care for either or both outcomes. We will test this hypothesis using the same longitudinal repeated measures analysis described for the primary outcomes at the 0.05 (2-sided) level of significance uncorrected for multiplicity. The difference between giving any intervention and usual care will be reported as least square means with 95% confidence intervals.

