11.4 Protocol Changes

Any change in the study protocol must be approved by the DSMB, PCORI, and the Project's Study Advisory Committee and approved by the cIRB and trial sites' before it can be implemented.

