Primary Outcome	Behavioral symptoms and resulting caregiver distress as measured by the NPI-Q Severity and Modified Caregiver Strain Index scales.

Primary Analysis	All analyses will be according to intent to treat. The analysis of the two primary outcomes – NPI-Q Severity and Modified Caregiver Strain Index scores – will be done using a longitudinal repeated measures analysis based on maximum likelihood methods adjusted for the stratified randomization by site. Treatment differences will be summarized by least square means and multiplicity corrected confidence intervals.
Secondary Outcomes	NPI-Q Distress, caregiver unmet needs and confidence, and caregiver depressive symptoms.
Tertiary Outcomes	Patient long-term nursing home placement, functional status, cognition, goal attainment scaling (GAS), “days spent at home”, Dementia Burden Scale-Caregiver, a composite measure of clinical benefit, Quality of Life of persons with dementia, Positive Aspects of Caregiving
Cost-effectiveness Analysis	Ratio of incremental net Medicare costs to incremental effects of the two primary outcomes, costs to Medicaid and consumers, changes in utilization by type of use, caregiver costs for spouses who have fee-for-service Medicare
Interim Analysis	Because this is a minimal risk trial with a relatively short follow-up period (18 months), no monitoring for efficacy or futility is proposed; only monitoring for safety will be done.

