### 9.4 Analysis of Secondary Outcomes

The analysis of the continuous secondary outcomes – NPI-Q Distress, caregiver depression (PHQ-8), Caregiver self-efficacy— will be analyzed like the primary outcomes. The Hochberg procedure will be used to control for the testing of each secondary outcome using an overall type I error of 5% (2-sided); treatment differences will be reported using 95% confidence intervals.

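### Should the 97.5% intervals for the primary treatment differences also be adjusted for the three pairwise comparisons?

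*SAP*

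**What the plan says.** The Primary Analysis row of the SAP synopsis states: "Treatment differences will be summarized by least square means and multiplicity corrected confidence intervals". The protocol synopsis has the same sentence. Neither says what the correction is for.

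The analysis sections give the level. SAP 9.3: "Treatment differences, averaged over all follow-up time points, will be summarized by least square means and 97.5% confidence intervals". Protocol 8.2.1 agrees: the differences "will be summarized by least square means and 97.5% confidence intervals".

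SAP 9.3 then gives the decision rule: "Significance testing for each outcome will be done by the Hochberg (1988) procedure using an overall type I error of 2.5% (2-sided"). The stated purpose is to control the three pairwise comparisons within each outcome, so that 2.5% per outcome holds the trial at 5%.

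The sample size counts both sources of multiplicity. SAP 6.1 uses 0.05/6 = 0.0083, "adjusted for 3 treatment comparisons (HSDC vs. CBDC, HSDC vs. UC and CBDC vs. UC) times 2 primary outcomes".

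For the secondary outcomes, SAP 9.4 runs Hochberg at 5% and says "treatment differences will be reported using 95% confidence intervals". In both sections the interval level is therefore one minus the alpha at which Hochberg is run.

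**The concern.** A reader who meets the synopsis first will expect intervals that carry the whole correction. The plan's own family has six members (three comparisons, two outcomes), and the intervals allow for only two. Where the plan leaves something uncorrected it usually says so: SAP 9.3 does this for the pooled any-intervention test, and SAP 9.3.1 for the extra demographic subgroups. The primary intervals carry no such note.

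At stake is the reading of a primary contrast whose interval excludes zero although Hochberg has not rejected it. Someone relying on the synopsis label could present that contrast as confirmed. The mismatch always runs in that direction, towards claiming a difference.

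**Working it through.** **Inputs.** SAP 6.1: SD 6.5 (NPI-Q Severity) and 6.7 (MCSI); differences of 1.5 (HSDC vs CBDC) and 3 (either program vs UC); 25% loss; 1000/1000/150. SAP 3: allocation 7:7:1. SAP 9.3: Hochberg at 0.025 per outcome, 97.5% intervals, estimand averaged across follow-up visits. SAP 6.1, below Table 2: effective censoring about 5%.

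**The plan's own figure.** 0.05/6 = 0.00833, as stated. With n = 2(z₁ + z₂)²·SD²/Δ², z₁ = 2.638 and z₂ = 1.645:
- MCSI: 2 × 4.283² × 44.89/2.25 = 732.01, so 733; 733/0.75 gives 978.
- NPI-Q Severity: 2 × 4.283² × 42.25/2.25 = 688.96, so 689; 689/0.75 gives 919.

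Both fit within the stated 1000 per arm.

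**What 97.5% corrects.** 1 − 0.05/2 = 0.975, critical value 2.241. Bonferroni over all six would be 1 − 0.05/6 = 99.17%, critical value 2.638. Width ratio: 2.638/2.241 = 1.18.

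**Joint coverage.** Three million simulated sets of the three contrasts under 7:7:1, known variance:
- At least one of three 97.5% intervals misses: 0.0598 (Bonferroni bound 3 × 0.025 = 0.075).
- Both outcomes, if independent: 1 − (1 − 0.0598)² = 0.116.
- Hochberg, any rejection under the global null: 0.0214, inside the 0.025 allowed.

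**When interval and test disagree.** A 97.5% interval excludes zero when p < 0.025. If the largest p is at most 0.025, Hochberg rejects all three and nothing conflicts. Otherwise there are two cases:
- Nothing is rejected, and the smallest p lies between 0.0083 and 0.025.
- The smallest p is rejected, and the second lies between 0.0125 and 0.025.

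Hochberg never rejects at p above 0.025, so a 97.5% interval cannot include zero for a rejected contrast.

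**How often, per outcome.** Column A uses one visit and 25% loss: 2150 × 7/15 × 0.75 = 752.5 per program, 2150/15 × 0.75 = 107.5 in UC, for SD 6.5 and 6.7. Column B is nearer the planned estimand: 1000/1000/150 less 5% = 950/950/142.5, and the mean of four complete visits. There SD = 6.7·√((1 + 3ρ)/4), which is 5.30 at ρ = 0.5 and 5.90 at ρ = 0.7. The documents do not give ρ, and four complete visits is optimistic, so column B is a lower-end case.

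| True means HSDC/CBDC/UC | A: one visit | B: visit average |
|---|---|---|
| 0/0/3 | 2.2–2.9% | 0.01–0.09% |
| 0/1.5/3 | 1.6–2.2% | 0.005–0.05% |
| 0/0/2 | 17.6–18.5% | 3.9–7.8% |
| 0/0/1.5 | 21.5–21.6% | 15.6–19.3% |

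Under the global null the rate is 4.2%. In 3.8% Hochberg rejects nothing at all (0.0598 − 0.0214 = 0.0384). In the rest it rejects one contrast but not another whose interval excludes zero.

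**What full correction would cost.** With 99.17% intervals, Hochberg can reject while the interval includes zero. In the one-visit setting this happens in 2.9–3.2% of trials at 0/0/3 and 17.5–17.7% at 0/1.5/3. At 0/1.5/3 that replaces a conflict of 1.6–2.2%. MCSI half-widths at 750/750/112.5 grow from 0.78 to 0.91 (HSDC vs CBDC) and from 1.52 to 1.79 (either program vs UC).

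**The case for a change.** The best case for a change is that the conflict is most frequent where it matters clinically. Protocol 6.1.1 puts the minimal important difference for MCSI at 1.5–2.3 points. If both programs beat usual care by 1.5, roughly one trial in five or six would show, for that outcome, an interval excluding zero without a Hochberg rejection, under either set of assumptions. SAP 9.3.1 also uses 99% intervals for the key subgroups under the same 2.5% alpha, so the authors were willing to go beyond 97.5%.

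The frequency at 1.5 units stands. Its consequence is limited. In that region nearly all conflicting contrasts are real differences: at 2.0 units in the one-visit setting, about 0.10 for each comparison with UC against 0.006 for the null contrast between programs. The interval is then not misleading about direction; the test simply fell short of its stricter threshold.

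The subgroup precedent is weak. Exact Bonferroni for six tests would be 1 − 0.025/6 = 99.58%, so 99% is not a full correction either.

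The labelling point also stands in part: the synopsis phrase is looser than it should be. But it is a summary of sections that state the level exactly, and it promises no simultaneous coverage over the three comparisons. The 2.5% and 5% set against the joint coverage above are test alphas, which the plan does not promise for its intervals.

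**Conclusion.** No change to the plan is needed. The intervals adjust for the two outcomes, the tests adjust for the two outcomes and the three comparisons, and SAP 9.3 bases significance on the tests. An analyst following it would report the Hochberg result beside each interval and would not call a contrast significant on the interval alone. Relabelling would alter no test, interval or conclusion, and would largely restate that rule.

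Full Bonferroni intervals are a trade-off without a clear gain. They restore joint coverage, but at 18% more width and with intervals that can contradict a rejection, which 97.5% intervals cannot do. Hochberg has no simple matching set of simultaneous intervals, so some mismatch has to be accepted.

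Timing also weighs against a change. SAP 9 says "The analytic plan will be modified as necessary up to final data lock and before study unblinding", and SAP 8 records the freeze of the primary and secondary data on 4/9/2024; whether that window is still open is unclear. For the protocol synopsis, "Any change in the study protocol must be approved by the DSMB, PCORI" and the other bodies named in Protocol 11.4.

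Size: joint non-coverage is about 6.0% per outcome. Conflict with the test is 4.2% under the global null, 0.01–2.9% at 3 units against UC with equal programs, and 15.6–21.6% at 1.5 units. These figures assume normal estimates with known variance, the plan's SDs and, at the lower ends, an assumed visit correlation of 0.5–0.7 with complete visits. The conclusion does not depend on them, because the confirmatory tests are sound in every scenario.
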